Data Collection from Survivors: Pre-visit, post-visit and 1 months - demographics, referrals to health services (including primary care and cardiology), CVH discussions, cardiovascular risk factor data

Primary Endpoint: Proportion of patients who consent to the study and complete the web-based heart health assessment.

1.0 Introduction and Background

Endometrial cancer is the most common gynecologic malignancy, and with approximately two-thirds of cases being diagnosed at an early stage it carries an excellent 5-year overall survival of approximately 95%.¹ Survivors of endometrial cancer are more likely to die of their comorbidities than their cancer, and cardiovascular disease (CVD) is not only the leading cause of death in the United States but has also been found to be the leading cause of death among endometrial cancer patients.²⁻⁴ This is likely due to the multiple overlapping risk factors for endometrial cancer and CVD including obesity and metabolic syndrome, elevating the importance of addressing cardiovascular (CV) health in routine survivorship care.^{5,6} Treatment of endometrial cancer adds to this risk, with a decrease in physical activity and subsequent weight gain during the post-operative period and concurrently undergoing adjuvant treatment with chemotherapy or radiation.

The National Comprehensive Cancer Network (NCCN) recommends assessment of CVD risk in their endometrial cancer survivorship guidelines.⁹ This is reinforced in the primary gynecologic oncology literature, with CVD risk assessment in patients with endometrial cancer suggested to be implemented as early in survivorship care as possible.² However, implementing this guideline in routine oncology practice may be challenging. Using survey data of over 1500 patients with breast, prostate, colorectal and gynecologic cancers, Weaver et al. found that one in three survivors with at least one CV risk factor reported no discussion of health promotion with their oncologic provider.¹⁰ Similarly, in a survey of 700 patients with a cancer diagnosis, Nicolaije et al. found that 35% of patient responded that they were minimally informed on how to improve their health, with 42% responding that they were completely uninformed on how to improve their health.¹¹ Ninety percent of oncologists in an electronic health record (EHR) tool pilot study (18 of 20) reported CV health discussions to be “somewhat” or “very” important; however, 58% “rarely” or “sometimes” discuss CV health with their patients.¹² As a result, oncologists make few referrals for CV care to primary care and cardiology for guideline-driven follow-up care.^{10,13-15}

Primary care is a key partner for managing CV health among cancer survivors. We are not aware of any studies specifically looking at primary care practitioner (PCP) utilization by endometrial cancer survivors, however, studies have shown that up to 20% of patients with a history of breast or colon cancer did not see a PCP within the first year of survivorship.^{7,8} Unsurprisingly, these patients were less likely to get preventative care and have chronic and general health issues managed than those who saw a PCP in addition to an oncology provider. Data from the original Automated Heart Health Assessment (AH-HA) team and others show that survivors want to have preventative discussions with their oncologists.¹⁶ Although some oncology providers are hesitant to address obesity and exercise in cancer survivors, exercise recommendations by providers increase cancer survivors’ physical activity by up to 30 minutes per week.¹⁷⁻¹⁹ Behavioral interventions for weight loss, exercise, diet, and smoking cessation, even if brief, can be successful in improving CV health among cancer survivors.²⁰⁻²⁵ For example, the odds of abstinence from smoking at 6 months increased 66% with provider lifestyle advice.²⁵

A pilot study to examine feasibility of a patient directed tool to assess heart health among endometrial cancer survivors

Wake Forest Baptist Comprehensive Cancer Center (WFBCCC)
WFBCCC # 99123

Web-based cardiovascular health assessment tools may play an important role in successful guideline implementation. The AH-HA tool, currently being tested in a large multi-site trial, is a provider facing EHR-embedded CV health assessment tool that renders a visual, interactive display of CVH risk factors, automatically populated from the EHR.²⁶ However, EHR integrated tools may require substantial time and cost for successful integration. A similar tool, named PREVENT, was developed by co-investigators on the proposed study using the American Heart Association (AHA) Simple 7 criteria for adolescent and young adult cancer patients, but is a web based, patient facing tool. This tool provides a graphic representation of the validated overall CV health score based on the Simple 7 risk factors²⁷, and provides behavior change recommendations to improve CV health. Provider and patient facing tools may offer implementation options to oncology clinics or be used as complementary strategies.

In this study, we will pilot an adapted version of the PREVENT tool for endometrial cancer survivors. This study will focus on the feasibility of using the PREVENT tool within routine follow-up care for endometrial cancer.

2.0 Objectives

2.1 Primary Objective

The primary objective of this *pilot* study is to assess the feasibility of enrolling and completing the heart health assessment among endometrial cancer patients scheduled for routine follow-up care.

2.2 Secondary Objectives

- 2.2.1 To assess patient satisfaction with the tool.
- 2.2.2 To identify the proportion of patients with non-ideal cardiovascular health scores who report initiating discussions regarding cardiovascular health during their routine oncology appointment.

3.0 Study Population

Endometrial cancer survivors presenting to WFBCCC for post-treatment surveillance visit.

3.1 Inclusion Criteria

- 3.1.1 Scheduled for a routine surveillance visit for pathologically confirmed stages I-IV endometrial cancer
- 3.1.2 ≥ 3 months post-potentially curative cancer treatment
- 3.1.3 Patients must be at least 18 years of age
- 3.1.4 Have a working email address
- 3.1.5 Comfortable reading medical information in English, as per self-report

3.2 Exclusion Criteria

- 3.2.1 Currently receiving treatment (e.g. radiation, chemotherapy, immunological treatments for endometrial cancer)
- 3.2.2 Have a history of endometrial cancer recurrence
- 3.2.3 Enrolled in hospice care or documentation of life expectancy < 6 months

3.3 Inclusion of Women and minorities

- 3.3.1 Women of all races and ethnicity who meet the above-described eligibility criteria are eligible for this trial. All of the participants will be women.

Minority Estimates: Similar to the national population data for cancer survivors and the demographics of the cancer patient population at the CCCWFU, non-Hispanic whites are expected to comprise the majority of our sample. Based on our cancer center data, we expect approximately 2% of included participants to be Hispanic/Latino (N=1). The breakdown of racial categories is expected to be as follows: 14% Black or African American (N=5), and 84% White (N=35), and 2% more than one race (N=1).

Should we not meet or exceed these estimates, the PI will engage the Office of Cancer Health Equity to discuss strategies to enhance recruitment in these target populations.

4.0 Methods

4.1 Registration Procedures

All patients entered on any WFBCCC trial, whether treatment, companion, or cancer control trial, **must** be linked with a study protocol in EPIC within 24 hours of Informed Consent. Patients **must** be registered prior to the initiation of the study.

You must perform the following steps in order to ensure prompt registration of your patient:

- 1.0 Complete the Eligibility Checklist (Appendix A)
- 2.0 Complete the Protocol Registration Form (Appendix B)
- 3.0 Alert the Cancer Center registrar by phone, *and then* send the Informed Consent Form, Eligibility Checklist and Protocol Registration Form to the registrar, either by fax or e-mail.

A pilot study to examine feasibility of a patient directed tool to assess heart health among endometrial cancer survivors

Wake Forest Baptist Comprehensive Cancer Center (WFBCCC)
WFBCCC # 99123

Contact Information:

Protocol Registrar PHONE [REDACTED]

Protocol Registrar FAX [REDACTED]

Protocol Registrar E-MAIL [REDACTED]

*Protocol Registration is open from 8:30 AM - 4:00 PM, Monday-Friday.

4.0 Fax/e-mail ALL eligibility source documents with registration. Patients **will not** be registered without all required supporting documents.

Note: If labs were performed at an outside institution, provide a printout of the results. Ensure that the most recent lab values are sent.

To complete the registration process, the Registrar will:

- assign a patient study number
- register the patient on the study

4.2 Experimental or Data Collection Methods

Data will be collected through patient surveys via REDCap, and the PREVENT tool, as well as via medical chart abstraction for lab values and vital signs.

4.2.1 EHR data extraction

Patient demographics (e.g., sex, date of birth, race/ethnicity) and the most recent risk factors for CVH (height, weight, fasting blood glucose, total cholesterol, blood pressure, smoking status) will be extracted at baseline (prior to clinic visit). Available EHR data will be uploaded into PREVENT prior to the clinic visit but may be updated within the PREVENT tool at the time of the clinic visit if updated values are attained. We acknowledge that not all patients will have updated information for CVH risk factors (fasting blood glucose, Hemoglobin A1c and total cholesterol). This pilot study is intended to determine what data are commonly available for a future study. We expect that height and weight will be the most commonly available data point.

A pilot study to examine feasibility of a patient directed tool to assess heart health among endometrial cancer survivors

Wake Forest Baptist Comprehensive Cancer Center (WFBCCC)
WFBCCC # 99123

4.2.2 Survey data

The pre-assessment survey will be sent electronically using REDCap to give the patient the option of completing the survey prior to the clinic visit. Alternatively, the patient may complete the questionnaire while in the waiting room at the clinic. The post-assessment survey will also be sent electronically using REDCap.

4.3 Study-Related Activities

	Screening^a	Pre-Visit Assessment^{a,b}	During Visit	Post-Visit Assessment^c (+ 14 Days)	1 Month Post-Visit^f (+/- 15 Days)
Eligibility	X				
Screen Failure Form	X				
Informed Consent		X			
Health Assessment		X		X	
Health Visit Information		X			
Health Knowledge Assessment		X		X	
Demographic & Health Behaviors		X			
Referral Assessment				X	
Tool Use			X ^e		
Tool Assessment				X	
Medical Record Data		X ^d			X

- a) Occurs pre-registration.
- b) Pre-visit assessment may be completed online via REDCap or on the day of study visit.
- c) Post-visit assessment should be completed at the end of study visit. If post-visit assessment cannot be completed at the end of the study visit, the assessment may be completed online by the patient via REDCap, ideally within 48 hours of study visit.
- d) Most recent patient vitals as well as fasting blood glucose, Hemoglobin A1c and total cholesterol will be extracted provided test results are within five years. Data extraction may be completed prior to visit or on day of study visit.
- e) This data will be collected directly in the tool and will not need to be entered in REDCap by staff.
- f) This is chart abstraction by staff, using the HER and data extraction form. There is no additional patient visit associated with this activity.

Basic Study Overview

This will be a single arm pilot study conducted at a single academic medical center (WFBCCC). We will identify, recruit, and consent endometrial cancer patients scheduled for a routine surveillance visit with a gynecologic

A pilot study to examine feasibility of a patient directed tool to assess heart health among endometrial cancer survivors

Wake Forest Baptist Comprehensive Cancer Center (WFBCCC)
WFBCCC # 99123

oncology provider. Patients will consent to the study and complete a brief questionnaire electronically prior to presenting for their office visit. Once they have been roomed in the office, a research team member will assist them in the use of the PREVENT tool, yielding a cardiovascular health score. Questions regarding the score will be directed towards their oncologic provider. They will then complete a brief questionnaire immediately after the visit. Chart review will be conducted 3 months after the visit.

Consent and Survey Administration: We will request a waiver of signed informed consent for the study (see Protection of Human Subjects). Potential participants identified from cancer center appointment schedules or referred by clinicians and navigators will be recruited by patient portal, phone, or in-person to complete brief web-based surveys before and after their regularly scheduled medical appointment. A record of screening failures will be captured Survey participants will receive a \$10 gift card.

Pre-Assessment Questionnaire: Prior to exposure to the PREVENT tool, we will ask 8 questions about CVH knowledge and perceived importance and appropriateness of heart health discussions during oncology care.

PREVENT Tool Interaction: While the patient is having their regularly scheduled medical appointment, the study coordinator will review their medical chart for cardiovascular risk information (weight, height, smoking status, blood pressure, total cholesterol, and hemoglobin A1c or fasting glucose). The most recent data will be entered in the PREVENT tool for the patient. We will help survivors access a patient-facing version of the PREVENT tool using a personal device or a study tablet computer. Survivors will use a personal email address to log-in to the patient-facing web application and will receive a welcome email after configuring their PREVENT profile. Patients will have the opportunity to review and update any of their cardiovascular risk information, as well as read information about cardiovascular health. The research coordinator will assist survivors in using the tool if requested.

Post-Assessment Questionnaires: Following survivor interaction with the PREVENT tool, survivors will complete:

- The same eight pre-assessment questionnaire along with three additional questions.
- We will additionally ask 5 questions regarding use of the PREVENT tool.

Collection of Post-Intervention Clinical Follow Up: Data will be collected about referrals, labs and new medications that occur during the 3-month period after their use of the study tool.

5.0 Outcome Measures

5.1 Primary Outcome

Proportion of patients who consent to the study and complete the web-based heart health assessment.

5.2 Secondary Outcomes

- 5.2.1 Secondary objective 2.2.1, patient satisfaction identified through post-visit survey with a 5-point Likert scale (strongly agree to strongly disagree) regarding liking the tool, helpfulness, ease of understanding and desire to use this tool with their oncologist.
- 5.2.2 Secondary objective 2.2.2, proportion of patients who report initiating discussions regarding cardiovascular health, identified through post-visit survey.

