6.3 Analysis of Secondary Outcomes

For secondary objective 2.2.1, patient satisfaction with the tool, one-sample t-tests will be used to test whether the average response to each question is greater than 3.5 (with three denoting a neutral response). Wilcoxon signed rank tests will be used to compare cancer survivors' knowledge regarding their cardiovascular health risk factors and perceived importance of cancer

A pilot study to examine feasibility of a patient directed tool to assess heart health among endometrial cancer survivors

Wake Forest Baptist Comprehensive Cancer Center (WFBCCC)
WFBCCC # 99123

and heart disease before and after using the CV risk visualization tool. Categorical comparisons will be evaluated with Fisher's Exact test.

For secondary objective 2.2.2, analyses will be largely descriptive (using means, medians, frequencies etc.).

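### Does objective 2.2.2 need a written cut-off and a missing-factor rule for a non-ideal cardiovascular health score?

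*Combined protocol and SAP*

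**What the plan says.** Objective 2.2.2 reads "To identify the proportion of patients with non-ideal cardiovascular health scores who report initiating discussions regarding cardiovascular health during their routine oncology appointment". The matching outcome in section 5.2.2 reads "Secondary objective 2.2.2, proportion of patients who report initiating discussions regarding cardiovascular health, identified through post-visit survey". It cites the objective by number but does not repeat the restriction to non-ideal scores. Section 6.3 adds only "For secondary objective 2.2.2, analyses will be largely descriptive (using means, medians, frequencies etc".

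On the score, section 1.0 says of the tool: "This tool provides a graphic representation of the validated overall CV health score based on the Simple 7 risk factors". The seven factors are not listed, and no boundary between ideal and non-ideal is given.

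On the inputs, section 4.2.1 says that "the most recent risk factors for CVH (height, weight, fasting blood glucose, total cholesterol, blood pressure, smoking status) will be extracted at baseline". The part of section 4.3 on interaction with the tool has the coordinator look up "cardiovascular risk information (weight, height, smoking status, blood pressure, total cholesterol, and hemoglobin A1c or fasting glucose". Section 4.2.1 also warns: "We acknowledge that not all patients will have updated information for CVH risk factors (fasting blood glucose, Hemoglobin A1c and total cholesterol", and adds "We expect that height and weight will be the most commonly available data point". Footnote d to the schedule in section 4.3 accepts laboratory results up to five years old.

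**The concern.** A proportion needs a defined denominator. Here it is the group with non-ideal scores, and the plan does not say in its own text how a patient enters that group. Two features make this look more than cosmetic.

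First, the score has seven factors by name, while each chart list has six items, or five factors if height and weight together serve one. Read alone, the lists suggest that no patient could have a complete score.

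Second, the plan itself expects gaps in glucose, HbA1c and cholesterol. One analyst might keep only complete scores. Another might class a patient as non-ideal as soon as any available factor falls short. The same data could then give two denominators and two percentages, and a rule chosen after seeing the data would leave the reported figure open to that choice.

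**Working it through.** The plan states no figure for objective 2.2.2. The check therefore covers where the score's inputs come from, and how far the result could move.

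**1. Is the score limited to chart data?**
- Chart lists (sections 4.2.1 and 4.3): height, weight, glucose or HbA1c, total cholesterol, blood pressure, smoking. That is 6 items, a shortfall of 7 − 6 = 1, or 7 − 5 = 2 if height and weight count as one factor.
- Section 4.2 names three data routes: REDCap surveys, the PREVENT tool and the chart. It assigns laboratory values and vital signs to the chart.
- The schedule in section 4.3 has a pre-visit form on demographics and health behaviors. Footnote e says that tool-use data are captured in the tool itself.
- Section 4.3 also has patients set up a profile in the tool and lets them review and change their risk information. The study overview there says that using the tool produces a score.

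The plan does not propose a chart-only score, so the shortfall of one or two factors does not show that scores will be incomplete. What remains is the expected absence of some laboratory values. The five-year window and the choice of HbA1c or fasting glucose reduce it but do not remove it.

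**2. Does section 5.2.2 change the population?**
It names objective 2.2.2, and the objective carries the restriction. If someone did use all assessed patients, let s be the share with ideal scores:

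all-patient rate − non-ideal rate = s × (rate in ideal − rate in non-ideal)

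The shift cannot exceed s. The documents give no value for s.

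**3. How far could the missing-factor rule move the figure?**
The base is the 37 assessed patients assumed in section 6.1. The plan's own precision statement reproduces: the exact (Clopper–Pearson) 95% interval for 18/37 is 31.9% to 65.6%, a half-width of 16.8 points against the stated 17.

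Let c be the share of complete scores and d the rate of initiating discussions among complete scores minus that among incomplete ones. Suppose all 37 are non-ideal under the broader rule, so that every complete score is non-ideal too. Then

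gap between the two rules = (1 − c) × d

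Both c and d are assumptions:

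| c | complete scores, 37 × c | d = 0 | d = 20 points | d = 40 points |
|---|---|---|---|---|
| 75% | 27.75, about 28 | 0 | 5 | 10 |
| 50% | 18.5, about 18 | 0 | 10 | 20 |
| 25% | 9.25, about 9 | 0 | 15 | 30 |

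Example: 11 of 18 complete and 7 of 19 incomplete patients initiate a discussion. The complete-only rule gives 11/18 = 61.1%. The broader rule gives (11 + 7)/37 = 48.6%. The gap is 12.5 points, which equals (19/37) × (61.1 − 36.8).

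Exact 95% half-widths near 50% are 16.8 points at n = 37, 19.4 at 28 (14/28), 24.0 at 18 (9/18) and 32.5 at 9 (4/9).

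For d up to 20 points every gap in the table is below 16.8 points. Only d = 40 with c at 50% or lower exceeds it. Nothing in the documents indicates which row or column applies.

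**4. What depends on the figure?**
Section 6.1 defines feasibility from completion of the web-based assessment. Section 6.3 attaches no test to objective 2.2.2. The sample size does not use it. Section 7.0 keeps the tool entries, surveys and chart extraction, so either rule can still be applied once data collection ends.

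**The case for a change.** The strongest case for a change is that the plan foresees missing inputs to the variable that defines its own denominator and states no rule, when a few sentences would do. A published cut-off would not by itself settle how a patient with a missing cholesterol value is classed. No passage says that the health-behaviors form feeds the tool or that patients must fill the gaps. No passage describes how scores held in Google Firebase are joined to answers in REDCap, although the linkage file in section 8.0 may serve.

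All of that is accurate, and it stands as an observation on brevity. It does not show a method that would give a wrong answer. The documents do not reveal how the tool treats a missing factor, so one cannot say that the rule is still open. A rule written without knowing this could make matters worse. A patient classed as non-ideal because any one available factor falls short may not be non-ideal on the tool's overall score, and it is the score that the objective refers to. Learning which values charts usually hold is also a declared aim of the pilot in section 4.2.1, so incomplete data are partly a finding in their own right.

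**Conclusion.** No change to the plan is needed. It does leave the cut-off and the handling of incomplete scores unstated, but this is operational detail that an analyst can fill sensibly: take the population from objective 2.2.2, use the classification that the tool or its cited source provides, and report the number of incomplete scores beside the proportion. The missing restriction in section 5.2.2 is editorial, because that section points to the objective. The comparison of six chart items with seven factors falls away, because surveys and the tool itself are stated data routes.

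The size cannot be fixed from the documents. Under the assumed ranges the two rules differ by 0 to 30 points, and by at most 15 points when the rates differ by no more than 20. A large difference needs both many incomplete scores and very different behavior in those patients, and the documents support neither assumption. Whatever the difference, it touches one descriptive secondary percentage in a pilot of at most 42 patients. The primary feasibility result and the sample size are unaffected. The conclusion assumes that the tool assigns a usable score to most patients. If it did not, the count of incomplete scores would show this.
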